4.3. Subject Number and Identification

Subjects will have a unique identification number used at Screening. Subjects will be assigned a subject number at the time of their randomization. Assignment of subject numbers will be in ascending order and no numbers will be omitted (eg, in Part A, Subjects 101, 102, etc., in Part B Subjects 201, 202, etc.). Replacement subjects ([Section 4.4](#)) will be assigned a subject number corresponding to the number of the subject he/she is replacing plus 1000 (eg, Subject 1101 replaces Subject 101).

Subjects will be identified by subject number only on all study documentation. A list identifying the subjects by subject number will be kept in the Site Master File.

4.4. Subject Withdrawal and Replacement

A subject is free to withdraw from the study at any time. In addition, a subject will be withdrawn if any of the following criteria are met:

- noncompliance with the study restrictions that might affect subject safety or study assessments/objectives, as considered applicable by the Investigator (or designee)
- any clinically relevant sign or symptom that, in the opinion of the Investigator (or designee), warrants subject withdrawal, including:
 - a serious adverse reaction (i.e., a SAE considered at least possibly related to OLP-1002 administration),
 - severe non-serious adverse reaction (i.e., severe non-serious AE considered to at least possibly related to OLP-1002 administration),
 - elevated AST, ALT, ALK (3 x ULN) or total bilirubin (2 x ULN),
 - QTcF increases > 60 msec compared to baseline (predose for Part A or Day 1 predose for Part B) and/or absolute QTcF values > 500 msec (confirmed by repeat measurement),
 - Tachycardia (> 150 beats/min) in the resting supine position (confirmed by 2 repeat measurements),
 - Severe hypertension (systolic blood pressure > 180 mmHg and/or diastolic blood pressure > 110 mmHg) in the resting supine position (confirmed by 2 repeat measurements).

If a subject is withdrawn, the Sponsor will be notified and the date and reason(s) for the withdrawal will be documented in the subject's electronic Case Report Form (eCRF). If a subject is withdrawn, efforts will be made to perform all follow-up assessments, if possible ([Appendix 6](#)). Other procedures may be performed at the Investigator's (or designee's) and/or Sponsor's discretion. If the subject is in-house, these procedures should be performed before the subject is discharged from the clinic. The Investigator (or designee) may also request that the subject return for an additional Follow-up visit. All withdrawn subjects will be followed until resolution of all their AEs or until the unresolved AEs are judged by the Investigator (or designee) to have stabilized.

Subjects who are withdrawn for reasons not related to study drug may be replaced following discussion between the Investigator and the Sponsor. Subjects withdrawn as a result of AEs thought to be related to the study drug will generally not be replaced.

4.5. Study Termination

The study may be discontinued at the discretion of the Investigator (or designee), Sponsor, or Sponsor's Medical Monitor if any of the following criteria are met:

- increased frequency, severity, and/or duration of known, anticipated, or previously reported AEs (this may also apply to AEs defined at Check-in as baseline signs and symptoms)
- medical or ethical reasons affecting the continued performance of the study
- difficulties in the recruitment of subjects
- cancelation of drug development.

5. STUDY TREATMENTS

5.1. Description, Storage, Packaging, and Labeling

Vials of OLP-1002 Injection Solution 100 µg/mL (1.5 mL in 5-mL vials) and the Diluent for OLP-1002 Injection Solution (5 mL in 10-mL vials) will be supplied by the Sponsor, along with the batch/lot number and Certificate of Analysis. The Diluent for OLP-1002 Injection Solution will also be used as the Placebo formulation. A certificate of batch certification and release, authorized by a Qualified Person in the European Union (EU) will also be issued, by a Covance CRU Qualified Person, for each batch of IMP imported into the EU.

The IMPs will be stored according to the instructions on the label at the CRU in a location that is locked with restricted access.

Dose solutions (OLP-1002 Injection Solution diluted with the Diluent for OLP-1002 Injection Solution) will be prepared by Covance CRU Pharmacy staff in accordance with instructions provided in the Pharmacy Manual. The Placebo formulation will be the Diluent for OLP-1002 Injection Solution without further manipulation.

5.2. Study Treatment Administration

Subjects will be administered the IMP in numerical order. OLP-1002 will be administered by SC injection in the upper arm. If subcutaneous dosing of OLP-1002 in the upper arm is not possible, the subject may be dosed in the abdomen at the Investigator's discretion. For subjects in Groups A2, A4, and A6, dosing will be on the opposite arm to the intradermal capsaicin test.

5.3. Randomization

The randomization code will be produced by the statistics department at Covance using a computer-generated pseudo-random permutation procedure. In Part A, 1 subject in groups

consisting of 4 subjects, and 2 subjects in groups consisting of 8 subjects, will be randomly assigned to receive placebo. In Part B, 2 subjects per group will be randomly assigned to receive placebo. All other subjects in a group will be randomized to receive OLP-1002.

Prior to the start of the study, a copy of the master randomization code will be supplied into the Covance CRU pharmacy staff (in sealed envelopes).

5.4. Blinding

The following controls will be employed to maintain the double-blind status of the study:

- The placebo solution will be identical in appearance to the OLP-1002.
- The Investigator and other members of staff involved with the study will remain blinded to the treatment randomization code during the assembly procedure.

To maintain the blind, the Investigator will be provided with sealed randomization code-break envelopes for each subject, containing details of their treatment. These individual sealed envelopes will be kept in a limited access area that is accessible 24 hours a day. In order to manage subject safety or to support dose-escalation decisions (in the event of possibly treatment-related SAEs or severe AEs), the decision to unblind resides solely with the Investigator. Whenever possible, and providing it does not interfere with or delay any decision in the best interest of the subject, the Investigator will discuss the intended code-break with the Sponsor. If it becomes necessary to break the code during the study, the date, time, and reason will be recorded in the subject's source data and on the individual envelope and will be witnessed by a second person.

5.5. Treatment Compliance

All doses of IMP will be administered by suitably qualified study site staff.

5.6. Drug Accountability

The Investigator (or designee) will maintain an accurate record of the receipt of the study supplies received. In addition, an accurate drug disposition record will be kept, specifying the amount dispensed to each subject and the date of dispensing. This drug accountability record will be available for inspection at any time. At the completion of the study, the original drug accountability record will be available for review by the Sponsor upon request.

For each batch of unit doses, the empty used unit dose containers will be discarded upon satisfactory completion of the compliance and accountability procedures. Any unused assembled unit doses will be retained until completion of the study.

At the completion of the study, all unused supplies will be returned to the Sponsor or disposed of by the study site, per the Sponsor's written instructions.

6. CONCOMITANT THERAPIES AND OTHER RESTRICTIONS

6.1. Concomitant Therapies

Subjects will refrain from use of any prescription medications/products from 14 days prior to dosing until the Follow-up visit, and non-prescription medications/products from 7 days prior to dosing until the Follow-up visit, unless the Investigator (or designee) and/or Sponsor have given their prior consent.

Paracetamol/acetaminophen (2 g/day for up to 3 consecutive days), hormone-replacement therapy, oral, implantable, transdermal, injectable, or intrauterine contraceptives are acceptable concomitant medications. The administration of any other concomitant medications during the study is prohibited without prior approval of the Investigator (or designee), unless its use is deemed necessary for treatment of an AE. Any medication taken by a subject during the course of the study and the reason for its use will be documented in the source data.

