13. Use or intend to use any prescription medications/products other than hormone-replacement therapy, oral, implantable, transdermal, injectable, or intrauterine contraceptive concomitant medications within 14 days prior to Check-in, unless deemed acceptable by the Investigator (or designee).
14. Use or intend to use slow-release medications/products considered to still be active within 14 days prior to Check-in, unless deemed acceptable by the Investigator (or designee).
15. Use or intend to use any nonprescription medications/products including vitamins, minerals, and phytotherapeutic/herbal/plant-derived preparations within 7 days prior to Check-in, unless deemed acceptable by the Investigator (or designee) and/or Sponsor have given their prior consent.
16. Use of tobacco- or nicotine-containing products within 3 months prior to Check-in.
17. Receipt of blood products within 60 days prior to Check-in.
18. Donation of blood from 3 months prior to Screening, plasma from 2 weeks prior to Screening, or platelets from 6 weeks prior to Screening.
19. Poor peripheral venous access.
20. Have previously completed or withdrawn from this study or any other study investigating OLP-1002, and have previously received the investigational product.
21. Subjects who, in the opinion of the Investigator (or designee), should not participate in this study.
22. Part A – PD assessment groups only
 - Subjects considered non-acceptable responders to the intradermal capsaicin test at screening, defined as maximum VAS score of < 3.0 or > 9.0.

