6.2. Diet

While confined at the study site, subjects will receive a standardized diet at scheduled times that do not conflict with other study-related activities. Subjects will be fasted overnight (at least 8 hours) before collection of blood samples for safety laboratory tests. On dosing days, subjects will receive a light breakfast approximately 2 hours prior to dosing. Meals will be provided as appropriate at other times and water will be freely available at all times.

Foods and beverages containing poppy seeds, grapefruit, or Seville oranges will not be allowed from 7 days prior to Check-in until the Follow-up visit.

Xanthine-containing foods and beverages will not be allowed from 36 hours before Check-in until Discharge from the site. Xanthine-containing foods and beverages will also not be allowed from 36 hours before non-residential site visits.

Chili pepper/hot sauce will not be allowed for 48 hours prior to Check-in for all subjects. Subjects in Groups A2, A4, and A6 will not be allowed chili pepper/hot sauce for 48 hours prior to their pre-screening visit.

Consumption of alcohol will not be permitted from 36 hours prior to Check-in until Discharge. Following discharge, up to 2 units/day of alcohol are permitted until 36 hours before each non-residential visit and the Follow-up visit.

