6.6. Other Restrictions

Subjects in Groups A2, A4, and A6 will not be allowed to shower within 1 hour prior to the capsaicin-evoked pain tests at prescreening, predose, and postdose.

Subjects will not be allowed to apply moisturizing creams or oils to the dosing site within 1 hour prior to dosing, or to the assessment site within 1 hour prior to the capsaicin-evoked pain test.

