8.2.2. Pharmacodynamic Population

The PD population will include all subjects who received at least 1 dose of OLP-1002 or placebo and for whom PD can be evaluated.

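### Paracetamol is allowed with no timing limit around the capsaicin and heat pain tests, although other influences on the capsaicin tests are controlled

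*Protocol*

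**What the plan says.** Section 6.1 restricts "non-prescription medications/products from 7 days prior to dosing until the Follow-up visit", unless prior consent is given. The next paragraph then names acceptable medications, beginning with "Paracetamol/acetaminophen (2 g/day for up to 3 consecutive days". It continues: "The administration of any other concomitant medications during the study is prohibited without prior approval of the Investigator (or designee". Paracetamol is therefore not among the drugs that need approval; its permission is standing and is capped by daily dose and duration only.

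The restrictions written for the capsaicin tests are elsewhere. Under Section 6.6, members of the three PD assessment groups "will not be allowed to shower within 1 hour prior to the capsaicin-evoked pain tests at prescreening, predose, and postdose", and creams or oils are barred from the test site for the same hour. Section 6.2 adds: "Subjects in Groups A2, A4, and A6 will not be allowed chili pepper/hot sauce for 48 hours prior to their pre-screening visit"; chili is also barred for 48 hours before Check-in for all subjects. Neither section mentions analgesics, and Sections 7.2 (capsaicin) and 7.3.5 (heat pain) set no analgesic-free period.

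The nearest eligibility rule is exclusion 15 in Section 4.2: "Use or intend to use any nonprescription medications/products including vitamins, minerals, and phytotherapeutic/herbal/plant-derived preparations within 7 days prior to Check-in". It has no paracetamol exemption, but the Investigator or Sponsor can waive it. Section 8.2.2 defines the PD population as "all subjects who received at least 1 dose of OLP-1002 or placebo and for whom PD can be evaluated".

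**The concern.** The PD question is whether OLP-1002 reduces evoked pain. Capsaicin pain, secondary hyperalgesia, heat pain threshold and heat pain tolerance are all listed in Section 2.2.2. A permitted analgesic can act on the same readings. Taken before the baseline test but not the postdose test, or the reverse, it enters the change from baseline and can imitate or hide a drug effect.

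The protocol protects the capsaicin tests against a shower an hour earlier but not against an analgesic, and gives no reason for the difference. A compromised reading cannot be replaced, because Section 3.4.2 caps capsaicin tests at three per subject: pre-screening, baseline and postdose.

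The readout has some uses. Section 1.6 says PD data will help set doses for later studies, and Sections 3.4 and 3.6 allow PD review before Part B and during escalation. Heat pain is also assessed under safety (Section 7.3.5).

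**Working it through.** The protocol gives no effect size, SD or power figure for PD (Sections 8.1 and 8.4), so there is no planned figure to reproduce. Two checks apply.

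**1. Which tests are covered by a rule that would keep paracetamol away?**

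| Test | Timing (Appendix 6) | Cover |
|---|---|---|
| Capsaicin, pre-screening | before Screening | none tied to the test; the Part A concomitant medication row starts at Screening |
| Capsaicin, baseline | Day -2, the day of Check-in | exclusion 15 (7 days before Check-in), waivable |
| Capsaicin, postdose | Day 2 (Section 3.4.2 says 48 hours postdose) | none; standing permission applies |
| Heat pain, Part A | Day 1 predose to 24 hours | none; standing permission applies |
| Heat pain, Part B | Screening; Days 1 and 13, predose to 24 hours | none tied to the test |

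**2. How far does one medicated subject move a group mean?**

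Let e be the individual effect of paracetamol on the reading. One user among n subjects shifts that mean by e/n. Group sizes are from Sections 3.1.1, 3.1.2 and 5.3.

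| Setting | Active : placebo | One placebo user | One active user |
|---|---|---|---|
| Capsaicin groups A2, A4, A6; Part B groups | 6 : 2 | e/2 | e/6 |
| Heat pain in A1, A3, A5, A7, A8 | 3 : 1 | e | e/3 |
| A2, A4, A6 pooled | 18 : 6 | e/6 | e/18 |

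Illustration only: suppose e on peak VAS lies between 0 and 1.5 points. This is an assumption; no document gives a value, and zero is possible. In a 6 : 2 group the placebo mean then moves by 0 to 1.5/2 = 0.75 points, and the active mean by 0 to 1.5/6 = 0.25 points.

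For scale, the standard error of an active-placebo difference is SD × √(1/n_placebo + 1/n_active):
- 6 : 2 gives SD × √(1/2 + 1/6) = 0.82 SD.
- 3 : 1 gives SD × √(1 + 1/3) = 1.15 SD.

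One placebo user shifts the difference by a full standard error only if e/2 ≥ 0.82 SD, that is e ≥ 1.64 SD, in a 6 : 2 group, or e ≥ 1.15 SD in a 3 : 1 group.

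Chance of at least one user around a given test, assuming independent use at rate p (also not in the documents), is 1 − (1 − p)^n:

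| p | of 2 placebo | of all 8 |
|---|---|---|
| 5% | 10% | 34% |
| 10% | 19% | 57% |
| 20% | 36% | 83% |

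**The case against.** The other side has a good deal.

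- **Baseline.** Exclusion 15 bears on the Day -2 test. This stands as partial cover, since it can be waived.
- **Residency.** Part A subjects are resident from Day -2 to Day 3 and Part B subjects from Day -1 to Day 15. Apart from capsaicin pre-screening and the Part B Screening heat test, every pain test falls inside those periods, and Section 6.1 requires all medication and its reason to be documented. Use would normally be visible and most likely for an adverse event. This stands and lowers the likely frequency, but visibility does not prevent use.
- **Left to the SAP.** How affected readings are summarised may well be. Permission to take the drug at test time is fixed in the protocol.

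A reader might also infer more than the text supports:

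- **Medicated readings necessarily stay in the PD population.** Section 8.2.2 turns on an undefined judgement of evaluability; it neither keeps nor drops them.
- **Pre-screening use biases the treatment comparison.** An altered score at the VAS limits of 3 and 9 can change who is enrolled. That precedes randomisation, and baseline is measured again on Day -2, so the randomised contrast is not affected by this route.
- **Pre-screening use is certainly unrecorded.** The blank schedule cell does not prove that. However, the use that matters precedes that visit, and so may fall outside a duty to document medication taken during the study.
- **One medicated subject sets the direction of effect.** With no effect size or SD this cannot be shown. Any outlier carries the same 1/n weight.

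**Conclusion.** The gap is real and modest. A stated rule permits an analgesic at the time of analgesia tests, and nothing in Sections 6.2, 6.6, 7.2, 7.3.5 or 8.2.2 closes it. The 1/n weights are exact: one medicated control moves its group's placebo mean by half the individual effect in capsaicin and Part B groups, and by the whole effect for heat pain in the five 4-subject Part A groups. The effect itself and the frequency of use are assumptions here.

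The endpoints are exploratory with descriptive analysis only, and none of the Section 3.7 stopping criteria uses them. The cost is a harder-to-interpret PD readout, with no consequence for an error rate or the primary safety endpoints. It should be corrected because correction is cheap, but it does not put the study in question.

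**What to change.** 1. Reconcile Section 6.1 with Section 6.6 so that the standing permission does not extend to discretionary analgesic use, meaning use not for an adverse event, in a window before each capsaicin test (including pre-screening) and each heat pain session. The sponsor sets the length of the window.
2. Add concomitant medication recording, including recent analgesic use, to the pre-screening column of the Part A schedule.
3. Leave treatment of adverse events unchanged; record the time of any analgesic given.
4. State in Section 8.2.2 or 8.4 that pain readings taken within the window are flagged, and that PD is summarised with and without them.

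Automatic exclusion is not advised. Analgesic use after dosing may itself relate to treatment, so dropping those readings is a post-randomisation exclusion that can bias the comparison. Losing one control also leaves 1 in a 6 : 2 group and none in a 3 : 1 group, where only the full summary and the individual listing would remain.

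Cost: a sentence in Section 6.1 or 6.6, one schedule entry and a sentence in Section 8. The downside is an occasional flagged reading and one extra summary.

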6.2. Diet

While confined at the study site, subjects will receive a standardized diet at scheduled times that do not conflict with other study-related activities. Subjects will be fasted overnight (at least 8 hours) before collection of blood samples for safety laboratory tests. On dosing days, subjects will receive a light breakfast approximately 2 hours prior to dosing. Meals will be provided as appropriate at other times and water will be freely available at all times.

Foods and beverages containing poppy seeds, grapefruit, or Seville oranges will not be allowed from 7 days prior to Check-in until the Follow-up visit.

Xanthine-containing foods and beverages will not be allowed from 36 hours before Check-in until Discharge from the site. Xanthine-containing foods and beverages will also not be allowed from 36 hours before non-residential site visits.

Chili pepper/hot sauce will not be allowed for 48 hours prior to Check-in for all subjects. Subjects in Groups A2, A4, and A6 will not be allowed chili pepper/hot sauce for 48 hours prior to their pre-screening visit.

Consumption of alcohol will not be permitted from 36 hours prior to Check-in until Discharge. Following discharge, up to 2 units/day of alcohol are permitted until 36 hours before each non-residential visit and the Follow-up visit.

6.3. Smoking

Subjects will not be permitted to use tobacco- or nicotine-containing products within 3 months prior to Check-in until the Follow-up visit.

6.4. Exercise

Subjects are required to refrain from strenuous exercise from 3 days before Check-in until the Follow-up visit and will otherwise maintain their normal level of physical activity during this

time (ie, will not begin a new exercise program nor participate in any unusually strenuous physical exertion).

6.5. Blood Donation

Subjects are required to refrain from donation of blood from 3 months prior to Screening, plasma from 2 weeks prior to Screening, and platelets from 6 weeks prior to Screening until 3 months after the Follow-up visit. Subjects should not be in receipt of blood products for 60 days prior to check-in.

6.6. Other Restrictions

Subjects in Groups A2, A4, and A6 will not be allowed to shower within 1 hour prior to the capsaicin-evoked pain tests at prescreening, predose, and postdose.

Subjects will not be allowed to apply moisturizing creams or oils to the dosing site within 1 hour prior to dosing, or to the assessment site within 1 hour prior to the capsaicin-evoked pain test.

7. STUDY ASSESSMENTS AND PROCEDURES

Every effort will be made to schedule and perform the procedures as closely as possible to the nominal time, giving considerations to appropriate posture conditions, practical restrictions, and the other procedures to be performed at the same timepoint.

The highest priority procedures will be performed closest to the nominal time. The order of priority for scheduling procedures around a timepoint is (in descending order of priority):

- dosing
- vital signs
- blood samples
- cardiac monitoring/ECG extractions
- any other procedures.

7.1. Pharmacokinetic Assessments

7.1.1. Sample Collection and Processing

Blood samples will be collected by venipuncture or cannulation at the times indicated in the Schedule of Assessments ([Appendix 6](#)). Furthermore, additional blood samples may be taken from each subject per treatment period, with the maximum volume of blood withdrawn per subject not exceeding the limit detailed in [Appendix 3](#). Any changes to the scheduled times of PK assessments will be agreed with the Sponsor and documented in the TMF. Samples taken from subjects who received placebo will not be analyzed.

In Part A, PK analysis will initially only be conducted for groups receiving $\geq 12 \mu\text{g}$ OLP-1002, with retrospective analyses of samples from lower dose groups occurring in the

event of PK data being quantifiable at doses $\geq 12 \mu\text{g}$ and if supported by bioanalytical stability data. In Part B, PK samples will be analyzed for all groups.

Procedures for collection, processing, and shipping of PK blood samples will be detailed in a separate document.

